##### **9.4.1.1 Efficacy Endpoint Analysis**

Descriptive statistics of the actual value and the percent change from baseline will be calculated at each time point for LDL-C.

Descriptive statistics of the actual value and the percent change from baseline will be calculated at each time point for non-HDL-C, TC, apo B, hsCRP, and HbA1c.

The number and percentage of subjects whose LDL-C value achieves the lipid management goals based on the risk assessment (<100 mg/dL [history of coronary artery

disease or heterozygous familial hypercholesterolemia], <120 mg/dL [high risk], or <140 mg/dL [intermediate risk]) will be calculated at each time point.

#### **9.4.1.2 Other Efficacy Endpoint Analysis**

Descriptive statistics of the actual value and the percent change from baseline will be calculated at each time point for HDL-C and TG.

#### **9.4.2 Safety Analysis**

Safety analyses will be performed using the safety analysis set by rollover subjects, newly enrolled subjects, and overall (rollover and newly enrolled) subjects. Baseline is defined as the last data before the start of IMP administration in the treatment period.

##### **9.4.2.1 Adverse Events**

All AEs will be coded by system organ class and Medical Dictionary for Regulatory Activities preferred term. The incidence of the following events will be summarized:

- Treatment-emergent AEs
- TEAEs by severity
- TEAEs causally related to the IMP
- TEAEs with an outcome of death
- Serious TEAEs
- TEAEs leading to discontinuation of the IMP
- TEAEs of special interest (including muscle-related TEAE and TEAE associated with hepatic impairment)

##### **9.4.2.2 Clinical Laboratory Data**

For parameters other than qualitative urinalysis, descriptive statistics of the actual value and change from baseline will be calculated at each time point. For qualitative urinalysis parameters, shift tables at each time point from baseline will be prepared. For parameters other than qualitative urinalysis, measured values will be categorized using the reference range to “below the lower limit of reference range,” “within the reference range,” and “above the upper limit of reference range,” and shift tables at each time point from baseline will be prepared.

The number and percentage of subjects meeting Criteria for Identifying Laboratory Values of Potential Clinical Relevance will be calculated.

#### **9.4.2.3 Physical Examination and Vital Signs Data**

Physical examination results will be tabulated.

For vital signs (blood pressure, pulse rate, and body temperature), descriptive statistics of the actual value and change from baseline will be calculated at each time point.

The number and percentage of subjects meeting Criteria for Identifying Vital Signs of Potential Clinical Relevance will be calculated.

#### **9.4.2.4 Electrocardiogram Data**

For ECG parameters (heart rate, PR interval, RR interval, QRS interval, QT interval, and QTcF), descriptive statistics of the actual value and change from baseline will be calculated at each time point. The number and percentage of subjects with an actual value of QTcF of >450 msec, >480 msec, or >500 msec at any postdose time point will be calculated. In addition, the number and percentage of subjects with a change from baseline in QTcF of >30 msec or >60 msec at any postdose time point will be calculated. Similarly, the number and percentage of subjects meeting these criteria at each postdose time point will also be calculated.

For assessment of normality/abnormality, shift tables at baseline and each time point will be prepared.

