b)		Statins + nonstatins	
 
Fibrates, selective PPAR<math>\alpha</math> modulators: From at least 6 weeks before
 
PCSK9 inhibitors: From at least 3 months before
 
Statins and drugs other than those above: From at least 4 weeks before
 
	
 
Statins: Same dose and regimen at (or below) the lowest approved dose
 
Nonstatins: Same dose and regimen
 

c)		Only nonstatins	
 
Fibrates, selective PPAR<math>\alpha</math> modulators: From at least 6 weeks before
 
PCSK9 inhibitors: From at least 3 months before
 
Drugs other than the above: From at least 4 weeks before
 
	Same dose and regimen

- 4) Patients with a history or current condition meeting any of the following criteria 1) to 3)

Category	History or current condition	LDL-C during the screening period
1)	History of coronary artery disease	$\geq 100$ mg/dL
	Heterozygous familial hypercholesterolemia (HeFH)	
2)	Peripheral arterial disease	$\geq 120$ mg/dL
	History of non-cardiogenic cerebral infarction	
	Chronic kidney disease (Provided that it does not fall under exclusion criterion 12))	
	Type 2 diabetes mellitus (Diagnosed at least 3 months before Week -2, without falling under exclusion criterion 7))	
3)	The total score in the coronary artery disease risk prediction model using the Suita score specified by the Japan Atherosclerosis Society is $\geq 56$ points (high risk)	$\geq 120$ mg/dL
	The total score in the coronary artery disease risk prediction model using the Suita score specified by the Japan Atherosclerosis Society is $\geq 41$ and $\leq 55$ points (intermediate risk)	$\geq 140$ mg/dL

- 5) Patients with fasting TG levels of <400 mg/dL at Week –2
- Rollover subjects from the phase 3 confirmatory trial
  - 1) Patients who provide written informed consent prior to the start of the trial
  - 2) Subjects who have completed the 12-week treatment period in the phase 3 confirmatory trial (Protocol No. 346-102-00002) and do not meet the discontinuation criteria for the IMP at Week 12

[Rationale for the inclusion criteria]

- Newly Enrolled Subjects
  - 1) This criterion is set based on ethical considerations.
  - 2) The lower limit of age is set as adults with sufficient ability to provide informed consent. The upper limit of age is set at 85 years in consideration of safety.

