#### **8.7.4 Electrocardiogram**

Electrocardiograms will be performed at the time points described in the Schedule of Assessments (Table 1.3-1) after resting for at least 10 minutes. The 12-lead ECG should be performed before blood collection whenever possible to minimize the effects on the assessment.

The investigator or subinvestigator will perform the ECG according to the procedures specified at each trial site and record the date of measurement, heart rate, PR interval, RR interval, QRS width, QT interval, and QTcF in the source document and the eCRF. The investigator or subinvestigator will determine normality/abnormality by the assessment of the measurements, and record the determinations in the source document and the eCRF. Any abnormal findings will be recorded in the source document and the eCRF. The subjects should be monitored for potentially clinically significant ECG findings. The sponsor may request to provide a copy of the ECG chart for any reason, including additional safety analysis.

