9.6 Electrocardiogram Data

For ECG parameters (heart rate, PR interval, RR interval, QRS interval, QT interval, and QTcF), descriptive statistics of the actual value and change from baseline will be calculated at each visit (Weeks 12, 24, 36, and 52).

The number and percentage of subjects with an actual value of QTcF of >450 ms, >480 ms, or >500 ms at any postdose time point will be calculated. In addition, the number and percentage of subjects with a change from baseline in QTcF of >30 ms or >60 ms at any postdose time point will be calculated. All data obtained after IMP administration will be analyzed, including those obtained at unscheduled visits. Similarly, the number and percentage of subjects meeting these criteria at each postdose time point will also be calculated.

For assessment of normality/abnormality, shift tables at baseline and each time point will be prepared.

The number and percentage of subjects meeting the criteria for identifying ECG measurements of potential clinical relevance ([Appendix 3: Criteria for Identifying ECG Measurements of Potential Clinical Relevance](#)) after IMP administration will be calculated. All data obtained after IMP administration will be analyzed, including those obtained at unscheduled visits.

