CT-10.4	Listing of Abnormal Laboratory Findings (Safety Analysis Set)
CT-10.5-1	Incidence of Potential Hy's Law Cases (Safety Analysis Set)
CT-10.5-2	Incidence of Potential Hy's Law Cases by Statin Response (Safety Analysis Set)
CT-10.6	Listing of Potential Hy's Law Cases (Safety Analysis Set)
CT-11.1-1	Descriptive Statistics for Vital Signs (Safety Analysis Set)
CT-11.1-2	Descriptive Statistics for Vital Signs by Statin Response (Safety Analysis Set)
CT-11.2-1	Incidence of Potentially Clinically Significant Abnormalities in Vital Signs (Safety Analysis Set)
CT-11.2-2	Incidence of Potentially Clinically Significant Abnormalities in Vital Signs by Statin Response (Safety Analysis Set)
CT-11.3-1	Descriptive Statistics for Body Weight (Safety Analysis Set)
CT-11.3-2	Descriptive Statistics for Body Weight by Statin Response (Safety Analysis Set)
CT-11.4-1	Incidence of Potentially Clinically Significant Abnormalities in Body Weight (Safety Analysis Set)
CT-11.4-2	Incidence of Potentially Clinically Significant Abnormalities in Body Weight by Statin Response (Safety Analysis Set)
CT-12.1-1	Descriptive Statistics for ECG Parameters (Safety Analysis Set)
CT-12.1-2	Descriptive Statistics for ECG Parameters by Statin Response (Safety Analysis Set)
CT-12.2-1	Categorical Analysis of ECG - QTcF (Safety Analysis Set)
CT-12.2-2	Categorical Analysis of ECG by Statin Response - QTcF (Safety Analysis Set)
CT-12.3-1	Shift Table of ECG Findings (Normal/Abnormal Assessments) (Safety Analysis Set)

- CT-12.3-2 Shift Table of ECG Findings (Normal/Abnormal Assessments) by Statin Response (Safety Analysis Set)
- CT-12.4-1 Incidence of Potentially Clinically Significant Abnormalities in ECG Parameters (Safety Analysis Set)
- CT-12.4-2 Incidence of Potentially Clinically Significant Abnormalities in ECG Parameters by Statin Response (Safety Analysis Set)
- CF-1-1 Percent Change From Baseline by Visit in Efficacy Parameters (Mean \pm SD) (Efficacy Analysis Set)
- CF-1-2 Percent Change From Baseline by Visit in Efficacy Parameters (Mean \pm SD) by Statin Response (Efficacy Analysis Set)

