Appendix 9 List of Subject Data Listings

DREAS-1	Discontinued Subjects and Reason for Discontinuation (Screened Subjects)
SUBEX-1	Subjects Excluded From Analysis Set (Screened Subjects)
DEMOG-1	Demographic Characteristics (Screened Subjects)
SMED-1	Investigational Medicinal Product Compliance (Screened Subjects)
SMED-2.1	Prior Hypercholesterolemic Treatment (Screened Subjects)
SMED-2.2	Hypercholesterolemic Treatment Compliance (Screened Subjects)
EFF-1.1	Listing of Primary Efficacy Endpoint - LDL-C (Efficacy Analysis Set)
EFF-1.2	Listing of Efficacy Endpoints Other Than LDL-C (Efficacy Analysis Set)
AE-1	Adverse Events (Informed Subjects)
LAB-1.1	Laboratory Values (Hematology) (Screened Subjects)
LAB-1.2	Laboratory Values (Blood Chemistry) (Screened Subjects)
LAB-1.3	Laboratory Values (Urinalysis) (Screened Subjects)
LAB-2	Laboratory Values (Fasting Lipid) (Screened Subjects)
PDATA-1	Study Completion Status and Reason for Discontinuation (Screened Subjects)
PDATA-2	Inclusion Criteria and Exclusion Criteria Not Met
PDATA-3.1	Medical History (Hypercholesterolemia) (Informed Subjects)
PDATA-3.2	Medical History (Screened Subjects)
PDATA-4	Physical Examination (Screened Subjects)
PDATA-5.1	Prior and Concomitant Medication (Screened Subjects)
PDATA-5.2	Prior and Concomitant Therapy (Screened Subjects)
PDATA-6	Vital Signs and Body Weight (Screened Subjects)
PDATA-7	12-Lead ECG Parameters and Findings (Screened Subjects)
PDATA-8	Pregnancy Test (Screened Subjects)
PDATA-9	TSH and Virus Test (Screened Subjects)

Protocol 346-102-00003

PDATA-10 Blood Draw Time for DNA storage (Screened Subjects)

PDATA-11 Screen Failures

PDATA-12 Post-treatment Follow-up (Screened Subjects)

PDEV-1 Protocol Deviations (Screened Subjects)

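### Within the ECG shift table (CT-12.3), a new rhythm or morphology finding in a subject already abnormal at baseline looks the same as no change

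*Protocol*

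**What the plan says.** Protocol 8.7.4 sets up a two-way reading: "The investigator or subinvestigator will determine normality/abnormality by the assessment of the measurements". No grade of clinical significance and no comparison with the baseline tracing is asked for. The same section collects the detail: "Any abnormal findings will be recorded in the source document and the eCRF".

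For analysis, Protocol 9.4.2.4 says "For assessment of normality/abnormality, shift tables at baseline and each time point will be prepared", and SAP 9.6 repeats it. SAP Appendix 8 lists the output as CT-12.3-1, "Shift Table of ECG Findings (Normal/Abnormal Assessments) (Safety Analysis Set", with CT-12.3-2 giving the same by statin response. Neither document plans a table by type of finding or a count of findings that are new since baseline. Among the planned outputs, the finding text appears only in the by-subject listing PDATA-7 (SAP Appendix 9).

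The numeric ECG data are handled separately. SAP 9.6 counts subjects above three QTcF thresholds, and does the same for change: "subjects with a change from baseline in QTcF of >30 ms or >60 ms at any postdose time point will be calculated". It adds a further count, "The number and percentage of subjects meeting the criteria for identifying ECG measurements of potential clinical relevance", using the heart rate, PR and QRS criteria in Appendix 3.

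**The concern.** A two-by-two shift table shows deterioration only in subjects who start normal. In a subject who starts abnormal, a new arrhythmia, ST-T change or Q wave is tabulated exactly like a stable old finding.

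Other safety domains leave more room for worsening from an abnormal start. Urine protein and glucose are flagged on a rise of at least 2 units (SAP Appendix 2), and vital signs, weight and ECG intervals have change-from-baseline criteria (SAP Appendices 1 and 3). The qualitative ECG reading has no equivalent.

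The 12-lead ECG is a listed endpoint of the primary safety objective (Protocol Section 3). Abnormal baseline tracings are plausible: the entry categories include "History of coronary artery disease" (Protocol 5.2.1), and newly enrolled subjects may be up to 85 years old. For rollover subjects the Week 12 results of the preceding double-blind trial serve as Day 1 results (Table 1.3-1, note b), so an abnormality that arose in that trial also counts as baseline-abnormal. What is at stake is the completeness of one descriptive table, not the validity of any test or estimate.

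**Working it through.** **Step 1: what the shift table can show.**

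| Baseline | Postdose | Shown in CT-12.3 | Possible meaning |
|---|---|---|---|
| Normal | Normal | No shift | No finding |
| Normal | Abnormal | Shift to abnormal | New finding |
| Abnormal | Normal | Shift to normal | Finding gone |
| Abnormal | Abnormal | No shift | Same finding, different finding, or old finding plus a new one |

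The last row merges three situations. The text recorded on the eCRF could separate them, but the table does not use it.

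**Step 2: where else a change would be counted in a subject abnormal at baseline.**

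| Type of change | Planned output |
|---|---|
| QTcF above 450, 480 or 500 ms, or a rise above 30 or 60 ms | Counted (SAP 9.6, CT-12.2) |
| Heart rate, PR or QRS past the criterion value and the required change | Counted (SAP Appendix 3, CT-12.4) |
| RR or QT interval | Descriptive statistics only (CT-12.1) |
| Any finding reported as an AE | Counted by SOC and PT (SAP 9.2) |
| Rhythm or morphology finding not reported as an AE | Listing PDATA-7 only |

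Only the last row is left without a summary.

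**Step 3: possible size.** The plan states no figure on this point, so there is none to reproduce. Inputs:

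- N = 120 treated subjects (Protocol 9.1; SAP Section 4).
- b = share abnormal at baseline. Not in the documents; assumed 10% to 50%.
- q = share who develop a new finding. Not in the documents; assumed 5% to 10%, the same whether baseline is normal or abnormal.

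Subjects who cannot contribute a normal-to-abnormal shift = N × b: 120 × 0.10 = 12, up to 120 × 0.50 = 60.

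Subjects with a new finding = N × q: 120 × 0.05 = 6, up to 120 × 0.10 = 12.

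New findings inside the abnormal-to-abnormal cell = N × b × q:

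- Low: 120 × 0.10 × 0.05 = 0.6
- Intermediate: 120 × 0.20 × 0.05 = 1.2; 120 × 0.30 × 0.10 = 3.6
- High: 120 × 0.50 × 0.10 = 6

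Two qualifications pull in opposite directions. If q counts every new finding, some of these subjects will also appear in the interval or AE tables, so the unsummarised number is smaller. If new findings are more common in subjects already abnormal, the number is larger.

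**The case against.** A reader might infer that a subject with an abnormal baseline ECG can never show a new ECG abnormality anywhere in the results. The documents do not support that. The QTcF, heart rate, PR and QRS counts ignore the baseline normal/abnormal reading and include unscheduled ECGs.

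The AE route does not depend on the baseline reading either. Protocol 8.8.1 defines an AE broadly and treats an event that continues from baseline and worsens as treatment-emergent. Protocol 8.8.2 assesses events against Day 1 and calls for a new AE entry when a condition worsens from then on. A clinically significant arrhythmia or ischaemic change should therefore reach the AE tables. It is true that 8.7.4 has no sentence turning ECG findings into AEs, unlike 8.7.2 for physical findings and 8.8.1 for laboratory values. It does, however, ask sites to monitor for potentially clinically significant ECG findings, so a reader should not conclude that these escape AE reporting.

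A reader might also infer that the table hides events mainly in the subjects at highest cardiac risk. That is plausible but has no figure behind it. Recent infarction, unstable angina, revascularisation, decompensated heart failure and torsade risk factors exclude newly enrolled subjects, and similar events during the confirmatory trial exclude rollover subjects (Protocol 5.2.2). The Japanese phase 2 trial reported no clinically significant changes in ECG parameters (Protocol 2.1), and no category in SAP Appendix 5 is cardiac.

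Finally, ECGs are performed by each site's own procedures and judged by the investigator. No central reading is described, and MedDRA coding is specified for AEs only. Naive matching of text could count a reworded old finding as new, and splitting finding types by every planned subgroup would leave almost empty cells.

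These arguments limit the scope and shape the remedy. They do not remove the point: the abnormal-to-abnormal cell mixes old and new findings, and no other summary separates them.

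**Conclusion.** The point holds within CT-12.3 only. A new rhythm or morphology finding that is not an interval or rate change, and that the investigator does not report as an AE, is indistinguishable there from an unchanged tracing if baseline was abnormal. Otherwise it can be seen only by reading PDATA-7.

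The gap is narrow and minor. The analysis is descriptive and uncontrolled, no data are lost, and no planned result becomes invalid. The range of 0.6 to 6 subjects out of 120 rests wholly on the assumed rates for b and q and on equal risk in both baseline groups. It illustrates the order of size and is not an estimate. The change is worth making because the ECG is a listed primary-safety endpoint and the information is already on the eCRF.

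**What to change.** In SAP 9.6, add to CT-12.3 the number and percentage of subjects with at least one postdose abnormal ECG finding not recorded at baseline, shown separately for subjects normal and abnormal at baseline. An equivalent layout divides the abnormal-to-abnormal cell into *same finding(s) only* and *new finding*.

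State three rules with it:

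- The finding text from the eCRF is grouped into prespecified categories.
- A finding is new only if its category was absent at baseline, so a reworded old finding is not counted.
- Counts by finding category are given for overall subjects only, to avoid very small cells.

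No new data, visit or protocol procedure is needed. The work is grouping text from the abnormal tracings among at most about 120 × 5 = 600 scheduled ECGs (baseline and Weeks 12, 24, 36 and 52), plus any unscheduled ones. The downsides are that coding effort and some spurious new findings from variable local reading. The split by baseline status and the listing let a reader check the latter.

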#### **9.4.2.5 Other Safety Data**

Descriptive statistics of the actual value and change from baseline will be calculated at each time point for body weight.

The number and percentage of subjects meeting Criteria for Identifying Body Weight of Potential Clinical Relevance will be calculated.

### **9.4.3 Other Analyses**

#### **9.4.3.1 Analysis of Demographic and Baseline Characteristics**

Frequency distributions or descriptive statistics of each item for demographic and other baseline characteristics will be calculated in each analysis set. The summarization will be performed by rollover subjects, newly enrolled subjects, and overall (rollover and newly enrolled) subjects.

#### **9.4.3.2 Pharmacokinetic Analysis**

No pharmacokinetic analysis is planned.

#### **9.4.3.3 Pharmacodynamic Analysis**

No pharmacodynamic analysis is planned.

#### **9.4.3.4 Pharmacokinetic/Pharmacodynamic Analysis**

No pharmacokinetic/pharmacodynamic analysis is planned.

#### **9.4.3.5 Pharmacogenomic Analysis**

No pharmacogenomic analysis is planned.

#### **9.4.3.6 Exploratory Endpoint Analysis**

Not applicable.

### **9.5 Interim Analysis and Adaptive Design**

Not applicable for interim analysis or adaptive design.

#### **9.5.1 Data Monitoring Committee**

Not applicable.

## **10 Supporting Documentation and Operational Considerations**

### **10.1 Appendix 1: Regulatory, Ethical, and Trial Oversight Considerations**

#### **10.1.1 Ethics and Responsibility**

This trial must be conducted in compliance with the protocol, applicable ICH (International Council for Harmonisation) GCP guidance, international ethical principles derived from the Declaration of Helsinki and Council for International Organizations of Medical Science guidelines, and applicable local laws and regulations. Each trial site will seek approval by an IRB according to regional requirements, and the trial site will provide that documentation to the sponsor. The IRB will evaluate the ethical, scientific, and medical appropriateness of the trial. Further, in preparing and handling the eCRF, IRE, and any safety information, the investigator, subinvestigator, and their staff will take measures to ensure adequate care in protecting subject privacy. To this end, a subject ID will be used to identify each subject.

Financial aspects, subject insurance, and the publication policy for the trial will be documented in the agreement between the sponsor and the trial site.

#### **10.1.2 Informed Consent**

Informed consent will be freely obtained from all subjects (or their guardian or legally acceptable representative, as applicable for local laws). The ICF will be approved by the same IRB that approves this protocol.

Each ICF will comply with the ICH GCP Guidelines, and local regulatory requirements.

In support of the site's standard process for administering informed consent, this trial will also allow for eICF as a tool within applicable regions and trial sites. The eICF utilizes the IRB approved site-specific ICF to offer subjects an enhanced platform to review and understand their rights as a research subject as well as required trial procedures. When possible, trial sites will have subjects review and sign the eICF prior to starting any trial procedures; however, if local regulations do not allow for use of the electronic format, subjects may continue in the trial utilizing the standard paper and wet ink signature process.

Investigators or subinvestigators may discuss trial availability and the possibility for entry with a potential subject without first obtaining consent. However, informed consent must be obtained and documented before initiation of any procedures that are performed

solely for the purpose of determining eligibility for this trial, including withdrawal from current medication(s).

Potential subjects are free to refuse entry into the trial, or withdraw from the trial at any time, without justification, and there will be no consequences to their further care.

Prospective trial subjects will be provided with controlled access to the eICF application by trial site staff. When the trial site staff and the subject agree that the subject has enough information to make an informed decision to participate, the subject will electronically sign in the eICF application of the trial site and an electronic date and timestamp will be applied to the signature. The subject will be given a printed, signed copy of the ICF. Any other parties required by the IRB (trial site staff, witnesses, or legally authorized representative) are also required to sign electronically and these signatures will be stored with the eICF in accordance with the ICH GCP Guideline and local regulatory requirements/guidelines. These signatures cannot be altered, removed, or copied. After the completion of the trial, the investigator or subinvestigator will store the electronic original (PDF) output from the eICF application.

For the paper ICF, once appropriate essential information has been provided and fully explained in layman's terms to the subject by the investigator/subinvestigator (or a qualified designee), and it has been documented that the subject has had the opportunity to ask questions, the IRB approved written ICF will be signed and dated by both the subject and the person obtaining consent (investigator/subinvestigator or designee), as well as by any other parties required by the IRB. The subject will receive a copy of the signed ICF; the original shall be kept on file by the investigator or subinvestigator.

Subjects may be asked to sign additional ICFs if the protocol is amended and the changes to the protocol result in additional information that needs to be provided to the subjects, so that they can make a knowledgeable and voluntary decision on continued trial participation. Female partners of male subjects who become pregnant during the course of the trial may be asked to sign additional ICFs in order to collect additional information regarding the non-subject partner and fetus.

A separate and similar consent process will be followed for the optional blood samples for FBR. Consent must be obtained before the blood sample is collected. Sample storage for FBR is optional and will not affect the subject's participation in the trial if the subject does not consent to the FBR sample storage.

